5.4 Safety Endpoints

Safety will be assessed by evaluation of the following variables:

- Treatment-emergent adverse events (TEAEs; frequency, severity, seriousness, and relationship to study drug)
- Clinical laboratory variables (hematology, biochemistry including liver enzymes and total bilirubin, and urinalysis)
- Vital signs (systolic and diastolic blood pressure and pulse rate)
- 12-lead electrocardiogram (ECG)
- Post Void Residual (PVR) Volume
- Acceptability and palatability questionnaires

5.4.1 Adverse Events

AEs will be coded using MedDRA. A TEAE is defined as an AE observed after starting administration of the IP until 30 days after the final administration of IP.

If the adverse event occurs on Day 1 and the onset check box on the (AE) eCRF is marked "Onset after first dose of study drug" or the onset check box is left blank, then the adverse event will be considered treatment emergent. If the adverse event occurs on Day 1 and the onset check box is marked "Onset before first dose of study drug", then the adverse event will not be considered treatment emergent. If a subject experiences an event both during the pre-investigational period and during the investigational period, the event will be considered as TEAE only if it has worsened in severity (i.e., it is reported with a new start date).

A drug-related TEAE is defined as any TEAE with at least a possible relationship to study treatment as assessed by the investigator or with missing assessment of the causal relationship.

An AE designated as serious by either the investigator or determined by Important Medical Event process will be summarized as an SAE. However, if the event is on IME list but medical monitor agrees with investigator that event is not SAE, then event can be downgraded.

Common TEAEs are defined as preferred terms (PTs) that have been reported by at least 5% of the subjects in any of the treatment groups.

When an AE start or stop date is missing, the date will be imputed using the rules in Section 6.10.2.2.

Adverse Events of Special Interest

Adverse Events of Special Interest include:

• Abnormal cardiac electrophysiology (including QTc prolongation), cardiac arrhythmia, and other cardiovascular adverse events

- Increased blood pressure as assessed through vital signs monitoring
- Hypersensitivity reactions
- Urinary retention
- Abnormal nervous system events: seizure, syncope, headache and dizziness

AEs of interest will be identified using all Preferred Terms (PT) from Standardized MedDRA queries (SMQ), see Table 2, or sponsor-defined list of search terms, see Appendix 9.2. Note: Most recent MedDRA version in which the AEs are coded will be used.

CV - Increased blood pressure	Hypertension SMQ – Narrow search
CV - QT prolongation	Torsade de pointes/QT prolongation SMQ – Broad search
CV - cardiac arrhythmia, cardiovascular adverse events	Arrhythmia related investigations signs and symptoms SMQ – Broad search, Supraventricular tachyarrhythmias (SMQ) – Broad search, Tachyarrhythmia terms nonspecific (SMQ) – Narrow search, Ventricular tachyarrhythmias (SMQ) -narrow search plus ventricular tachycardia
Hypersensitivity reactions	Hypersensitivity SMQ – Narrow search
Seizure	Lower Level Term 10039906
Syncope	Syncope SMQ – Narrow search (also included as part of the CV - Increased heart rate, tachycardia, atrial fibrillation, and palpitations) PT 10042772
Headache	Headache PT 10019211
Dizziness	Dizziness PT 10013573

Table 2Standardized MedDRA Queries

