7.3.6 Adverse Events of Special Interest

Adverse Events of Special Interest include:

- Increased blood pressure
- Cardiac electrophysiology (including QTc prolongation) and cardiac arrhythmia (including increased heart rate, tachycardia, atrial fibrillation and palpitations)
- Hypersensitivity reactions
- Urinary retention
- Hepatotoxicity
- Seizure/syncope

AEs (serious or nonserious) of special interest are to be collected via the SAE worksheet and reported within 24 hours as described in [Appendix 12.4.5 Reporting Procedures for Serious Adverse Events].

Sponsor: APGD EudraCT number 2016-001767-37 - CONFIDENTIAL -

ponsor: APGD ISN/Protocol: 178-CL-204

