The number of TEAEs and the number and percentage of subjects with TEAEs, as classified by SOC and PT will also be summarized by severity and by relationship to study drug. In the subject count, if a subject has multiple TEAEs with the same SOC or PT, but with differing severity or relationship, then the subject will be counted only once with the worst severity and highest degree of relationship, however, if any of the severity or relationship values are missing then the subject will be counted only once with missing severity or relationship. In the adverse event count, the adverse events will be presented in each category they were classified to. Drug related TEAEs will be presented in a similar way by severity only.

Adverse events of interest will be tabulated by PT.

AEs will be provided in listing format by country, site and subject for the SAF.

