6.5.2.2 Liver Safety Assessment

The liver safety assessments will be summarized by the categories below based on the measurements from Alkaline Phosphatase (ALP), Alanine Transaminase (ALT), total bilirubin, Aspartate Transaminase (AST) and their combination. These parameters will be based on measurements from a central laboratory.

The subject's highest value during the investigational period will be used.

- ALT >3xULN, >5xULN, >10xULN, >20xULN
- AST >3xULN, >5xULN, >10xULN, >20xULN
- ALT or AST >3xULN, >5xULN, >10xULN, >20xULN
- ALP > 1.5 xULN
- Total Bilirubin >2xULN
- (ALT or AST >3xULN) and Total Bilirubin >2xULN
- (ALT or AST >3xULN) and ALP <2xULN and Total Bilirubin >2xULN

The last 2 criteria where 2 or more parameters are evaluated will be with the measurements on the same day or up to 1 day apart (Samples to be taken simultaneously or within a maximum of 24 hours).

The denominator for each criterion will be the number of subjects who have at least one value during the investigational period. The number and percentage of subjects meeting the criteria during the investigational period will be summarized, within and across age group by treatment group.

A scatter plot of Peak AST or ALT data vs. Peak Total Bilirubin data will be presented for mirabegron subjects. Data will be presented as fractions of the ULN. In this scatter plot the area for Hy's Law will be presented, where ALT or AST >3xULN and Total bilirubin > 2xULN (ALT, ALT and Total Bilirubin from same blood sample or within a maximum of 24 hours). The area for hyperbilirubinemia (ALT and AST <3xULN and Total bilirubin >2xULN), Temple's corollary (ALT or AST >3xULN and Total bilirubin < 2xULN) will also be presented in this scatter plot.

Laboratory data will be provided in listing format by country, site and subject for the SAF.

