9.2 AEs of Interest not covered by Standard MedDRA SMQs latest Version

The following is a list of AE terms to programmatically flag subjects with AE's of interest (see Section 5.4.1).

Туре	Term	Code	AE of Interest	MedDRA 24.0 or Higher Search Criteria
LLT	Acute retention of urine	10001055	Acute urinary retention	Selected LLT (non-SMQ)
PT	Residual urine volume	10050832	Urinary retention	Selected PT's (non-SMQ)
PT	Residual urine volume increased	10067758	Urinary retention	Selected PT's (non-SMQ)
PT	Urinary retention	10046555	Urinary retention	Selected PT's (non-SMQ)

Note: Most recent MedDRA version in which AEs are coded will be used.

9.3 2017 American Academy of Pediatric Clinical Practice Guidelines

From 2017 (American Academy of Pediatric) Clinical Practice Guidelines, Table 4, Males, see Reference Flynn, et al, 2017

		Systolic Blood Pressure (mmHg)							Diastolic Blood Pressure (mmHg)						
Age	BP	Percentiles							Percentiles						
(years)	Percentile	5 th	10 th	25 th	50 th	75 th	90 th	95 th	5 th	10 th	25 th	50 th	75 th	90 th	95 th
5	Height (cm)	104.4	106.2	109.1	112.4	115.7	118.6	120.3	104.4	106.2	109.1	112.4	115.7	118.6	120.3
	90 th	103	104	105	106	107	108	108	63	64	65	65	66	67	67
	95 th	107	108	109	109	110	111	112	66	67	68	69	70	70	71
	95th+12mmHg	119	120	121	121	122	123	124	78	79	80	81	82	82	83
6	Height (cm)	110.3	112.2	115.3	118.9	122.4	125.6	127.5	110.3	112.2	115.3	118.9	122.4	125.6	127.5
	90 th	105	105	106	107	109	110	110	66	66	67	68	68	69	69
	95 th	108	109	110	111	112	113	114	69	70	70	71	72	72	73
	95th+12mmHg	120	121	122	123	124	125	126	81	82	82	83	84	84	85
7	Height (cm)	116.1	118	121.4	125.1	128.9	132.4	134.5	116.1	118	121.4	125.1	128.9	132.4	134.5
	90 th	106	107	108	109	110	111	111	68	68	69	70	70	71	71
	95 th	110	110	111	112	114	115	116	71	71	72	73	73	74	74
	95th+12mmHg	122	122	123	124	126	127	128	83	83	84	85	85	86	86
8	Height (cm)	121.4	123.5	127	131	135.1	138.8	141	121.4	123.5	127	131	135.1	138.8	141
	90 th	107	108	109	110	111	112	112	69	70	70	71	72	72	73
	95 th	111	112	112	114	115	116	117	72	73	73	74	75	75	75
	95th+12mmHg	123	124	124	126	127	128	129	84	85	85	86	87	87	87
9	Height (cm)	126	128.3	132.1	136.3	140.7	144.7	147.1	126	128.3	132.1	136.3	140.7	144.7	147.1
	90 th	107	108	109	110	112	113	114	70	71	72	73	74	74	74
	95 th	112	112	113	115	116	118	119	74	74	75	76	76	77	77
	95th+12mmHg	124	124	125	127	128	130	131	86	86	87	88	88	89	89
10	Height (cm)	130.2	132.7	136.7	141.3	146.9	150.1	152.7	130.2	132.7	136.7	141.3	146.9	150.1	152.7

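### The SAP leaves hepatotoxicity out of its adverse events of interest although the protocol lists it, so that tabulation has no means of identifying reported hepatic events

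*SAP*

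**What the plan says.** **Protocol 7.3.6** lists the adverse events of special interest: increased blood pressure, cardiac electrophysiology and arrhythmia, hypersensitivity, urinary retention, "Hepatotoxicity", and seizure or syncope. The reporting rule is "AEs (serious or nonserious) of special interest are to be collected via the SAE worksheet and reported within 24 hours as described in" Appendix 12.4.5.

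**SAP 5.4.1** gives its own list: cardiac events, increased blood pressure, hypersensitivity, urinary retention, and "Abnormal nervous system events: seizure, syncope, headache and dizziness". It then fixes how the events are found: "AEs of interest will be identified using all Preferred Terms (PT) from Standardized MedDRA queries (SMQ), see Table 2, or sponsor-defined list of search terms", the latter being Appendix 9.2.

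**SAP Table 2** holds the searches, for example "Hypersensitivity SMQ – Narrow search". **SAP Appendix 9.2** opens with "The following is a list of AE terms to programmatically flag subjects with AE's of interest" and gives four terms.

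**SAP 6.5.1** states the output for this group of events: "Adverse events of interest will be tabulated by PT".

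**SAP 6.5.2.2** handles liver safety separately, through ALT, AST, ALP and total bilirubin thresholds. It says of them: "These parameters will be based on measurements from a central laboratory".

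**The concern.** The protocol asks sites to report hepatotoxicity on the expedited route even when it is not serious, so it treats the category as one to watch. The SAP turns the other five categories into searches and a tabulation, and gives this one neither.

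What is at stake is pre-specification. If hepatic events are reported, someone must decide which preferred terms count as hepatotoxicity. With no search named in the SAP, that choice would be made after the data are seen, and possibly after treatment codes are open. For the other categories the choice is already fixed.

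**Working it through.** No sample size, error rate or event count bears on this point, so the check is a comparison of lists.

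**Step 1. Categories.**

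| Protocol 7.3.6 | SAP 5.4.1 | Search in Table 2 or Appendix 9.2 |
|---|---|---|
| Increased blood pressure | Yes | Table 2 |
| Cardiac electrophysiology and arrhythmia | Yes, with other cardiovascular events added | Table 2 (two rows) |
| Hypersensitivity | Yes | Table 2 |
| Urinary retention | Yes | Appendix 9.2 (four terms) |
| Seizure/syncope | Yes, with headache and dizziness added | Table 2 (four rows) |
| Hepatotoxicity | No | None |

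The protocol has 6 categories and the SAP has 5. All five SAP categories match a protocol category, so 6 − 5 = 1 has no counterpart, and it is hepatotoxicity.

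**Step 2. Search terms.** Table 2 has 1 + 2 + 1 + 4 = 8 rows, none hepatic. Appendix 9.2 has 4 terms, all for urinary retention or residual urine volume. That is 0 hepatic entries out of 8 + 4 = 12.

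**Step 3. Could a hepatic event enter by another route?** SAP 5.4.1 introduces its list as what the events include, which could be read as open-ended. The identification rule that follows is not open-ended: it names only Table 2 and Appendix 9.2. An event outside both has no stated way into the 6.5.1 tabulation.

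**Step 4. Is a reason recorded?** The two change lists in SAP 7.1 and 7.2 each have entries for 5.4.1. These concern the definitions of treatment-emergent, common and serious events, not the special-interest list. An omission dating from SAP version 1.0 would not show in these lists, so they show only that no reason is given in the supplied documents.

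**Step 5. What else covers the liver?**

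- *General adverse event tables (SAP 6.5.1).* All, drug-related, serious and treatment-discontinuation events are tabulated by system organ class and preferred term, by arm. Hepatic terms appear there, but nothing says which terms make up hepatotoxicity.
- *Liver laboratory tables (SAP 6.5.2.2).* Subjects above each threshold are counted by arm, within and across age groups. These are laboratory values, not reported events. They come from the central laboratory only, whereas SAP 6.5.2.1 and Protocol Table 12 provide for local results. The scatter plot showing the Hy's law area covers mirabegron subjects only.
- *Timing.* Protocol 7.2.2 schedules on-treatment blood sampling at weeks 4 and 12, with week 14 tests only if triggered. Adverse events are collected to 30 days after the last dose (Protocol 7.3.1). Reported events therefore cover time that scheduled sampling does not.

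**Step 6. Would adding a search be enough?** Not for a count per category. SAP 6.5.1 commits only to tabulation by preferred term. A hepatic row in Table 2 would yield separate preferred-term lines, and two subjects with different hepatic terms would sit on two lines. A single count needs a change to 6.5.1, and the same applies to the five categories already listed.

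**The case against.** The best case for leaving the SAP alone has four parts.

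1. *Protocol 7.3.6 is a rule on collection and reporting.* The protocol's own adverse event analysis section (9.5.1) asks for no special-interest tabulation, and Appendix 12.5 delegates only liver enzyme analyses to the SAP, which supplies them. This stands as far as it goes: the SAP does not fail to run an analysis the protocol specified. But the SAP chose to tabulate these events and carried over every category except one.
2. *Liver injury is already analysed by arm.* SAP 6.5.2.2 gives threshold counts, and Protocol 12.4.1.2 requires potential Hy's law cases to be reported as important medical events, which brings them into the serious event tables. This limits the harm considerably. The remaining gap is narrower: reported hepatic events as a defined group, including those without a qualifying central-laboratory value.
3. *Hepatotoxicity is not among the identified or potential risks in Protocol 2.1.3.* That is correct and lowers the priority. The protocol nonetheless put it on the special-interest list.
4. *The list may have changed later.* The SAP refers to protocol version 3 or higher, if applicable, and the supplied protocol is version 2.0. A later list cannot be excluded, but none is in the documents and the SAP cites none.

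A reader might go further and infer that hepatic events go uncollected or disappear from the report. The documents do not support that: the SAP leaves collection untouched, and the general tables carry every treatment-emergent event. A reader might also infer that one added row in Table 2 would give a grouped hepatic count. Step 6 shows that it would not.

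**Conclusion.** The mismatch is real and specific. One of the six special-interest categories in the protocol has no entry in the SAP list, no search among the 12 entries provided, and no recorded reason. As written, the tabulation in SAP 6.5.1 cannot identify reported hepatic events. The general adverse event tables and the liver laboratory summaries reduce the consequence but are not a pre-specified summary of reported hepatic events.

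Severity is minor to moderate, and the primary endpoint is unaffected. The documents give no hepatic event rate, so no expected number of affected subjects can be stated. The conclusion assumes that Protocol version 2.0, as supplied, still sets the special-interest list.

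**What to change.** Make three changes before unblinding:

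1. Add hepatotoxicity to the list in SAP 5.4.1.
2. Add a named hepatic search, either a standardised MedDRA query or a sponsor-defined list of preferred terms, to Table 2 or Appendix 9.2.
3. Amend SAP 6.5.1 so that events of interest are tabulated by category, giving the number and percentage of subjects with at least one event by arm, as well as by preferred term.

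If the sponsor means laboratory thresholds alone to cover the liver, the SAP should say so and justify the departure from Protocol 7.3.6.

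The cost is one search row and one subtotal line per category. No new data are needed, because the protocol already collects these events.

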5.4.2 Vital Signs

5.4.2.1 Clinical Measurement of Vital Signs

Single blood pressure, pulse and body temperature measurements will be performed at visit 1/screening, visit 3/baseline, visit 5/week 4, visit 7/week 12 (EoT), and visit 8/week 14 (EoS). Clinic measurements of vital signs at visit 1/screening and visit 3/baseline will be used to assess eligibility.

The preferred method of blood pressure measurement is via the auscultatory technique. If this method is not available at the study site, measurements will be per standard clinic practices.

Single measurements of pulse and body temperature will be measured in the sitting position (when possible, otherwise supine, but always in the same position).

For subjects enrolled under:

• Protocol version 1 and 2, one single blood pressure measurement will be taken.

• Protocol version 3 or higher (if applicable), at least two blood pressure measurements will be taken separated by 5 minutes and the average of these measurements will be the documented blood pressure.

5.4.2.2 Self-Measurement of Vital Signs

Self-blood pressure monitoring (SBPM; SBP and DBP) will be measured at visit 2/week 2, visit 3/baseline, visit 4/week 2, visit 5/week 4, visit 6/week 8, and visit 7/week 12 (EoT) and whenever deemed necessary by the investigator.

SBPM will be measured once in the morning and evening during the 2-day Weekend Episodic Diary collection period. Measurements will be taken in the sitting position (when possible, otherwise supine, but always in the same position). Preferably, the right arm should be used. Morning measurement should be taken before IP intake and evening measurement should be taken prior to bedtime.

5.4.2.3 Conversion of Blood Pressure to Percentiles

Both the systolic and diastolic blood pressure site measurements will additionally be converted to percentiles specific to the age (years), sex and height (cm) of the subject using the following steps [NIH, 2005]:

- The height of a subject is measured at screening and baseline. Height at baseline will be used.
- Let Z = the z-score (i.e. the number of standard deviations above or below the mean) of the height (cm) of the subject at the study visit relative to healthy subjects of the same age and gender using CDC growth charts [CDC, 2000]. The SAS code to calculate this is located on the Centers for Disease Control (CDC) and Prevention website: https://www.cdc.gov/nccdphp/dnpao/growthcharts/resources/sas.htm.
- Let BP = the blood pressure (mmHg) that is being converted (either systolic or diastolic) and Y=the age of the child in years.
- Taking the coefficients from the appropriate column in Table 3 below, compute Z_{BP}, the Z-score for the blood pressure:

$$Z_{BP} = \left[BP - \alpha - \sum_{j=1}^{4} \beta_j (Y - 10)^j - \sum_{k=1}^{4} \gamma_k Z^k \right] / \sigma$$

- If $\Phi(.)$ is the area under the standard normal curve to the left of Z, calculate P, the gender, age and height specific percentile of the blood pressure as $P=\Phi(Z_{BP})*100\%$.
- The exact age at a visit will be calculated as:

$$Age = \frac{(D_V - D_B + 1)}{365.25}$$

where D_v is the visit date and D_B is the subject's date of birth. When the exact age at a visit is missing and cannot be calculated because of a missing date of birth, but where the

age entered at screening is known only to be Y years (an integer), the percentile will be calculated for age=Y+0.5.

			Systolic BP		Diastolic BP	
Variable		Symbol	Male	Female	Male	Female
Intercept		Α	102.19768	102.01027	61.01217	60.50510
Age	(Age-10)	β1	1.82416	1.94397	0.68314	1.01301
	$(Age-10)^2$	β2	0.12776	0.00598	-0.09835	0.01157
	$(Age-10)^{3}$	β3	0.00249	-0.00789	0.01711	0.00424
	(Age-10) ⁴	β4	-0.00135	-0.00059	0.00045	-0.00137
Height	Z	γ1	2.73157	2.03526	1.46993	1.16641
Z-Score	Z^2	γ2	-0.19618	0.02534	-0.07849	0.12795
	Z^3	γ3	-0.04659	-0.01884	-0.03144	-0.03869
	Z^4	γ4	0.00947	0.00121	0.00967	-0.00079
Standard Deviation		σ	10.7128	10.4855	11.6032	10.9573

 Table 3
 Coefficients for Conversion of Blood Pressure to Percentiles

5.4.2.4 Pulse Rate in Relation to Age

Resting pulse rate will be compared to age-related norms [Fleming et al., 2011] according to the percentiles shown in Table 4.

Age	Percentile								
	1 st	10 th	25 th	50 th	75 th	90 th	99 th		
4-6y	65	81	89	98	108	117	131		
6-8y	59	74	82	91	101	111	123		
8-12y	52	67	75	84	93	103	115		
12-15y	47	62	69	78	87	96	108		
15-18y	43	58	65	73	83	92	104		

 Table 4
 Percentiles for Resting Pulse Rate in Relation to Age and Gender

Source: web appendix to the Fleming et al article (web table 5)

Each value of pulse rate will be categorized as either being above the age-specific 99th percentile or below the 1st percentile.

5.4.2.5 Body Temperature

Body Temperature will be compared to a reference range of 35.4 to 37.7 degrees Celsius [Kliegman et al, 2007].

5.4.3 Clinical Laboratory Variables

Hematology, biochemistry and urinalysis assessments will be taken at visit 1/week -4 (screening), visit 5/week 4, and visit 7/week 12 (EoT). Additional hematology, biochemistry and urinalysis tests will be performed at visit 3/week 0 (baseline), and visit 8/week 14 (EoS) only if an AE related to hematology, biochemistry or urinalysis parameters occurred since the previous visit or at the discretion of the investigator.

All clinical laboratory assessments will be performed at a central laboratory or at a local laboratory if results can be made available to the investigative site (see protocol, Appendix 12.23, Table 11), except for urine pregnancy testing and urinalysis (urinalysis dipstick), which will be performed at a local laboratory. Pregnancy test in females of child bearing potential will be performed in serum at screening, at baseline, visit 5/week 4, visit 7/week 12 (EoT), and visit 8/week 14 (EoS).

Additional hematology, biochemistry and urinalysis (UA dipstick) tests will be performed at visit 3/week 0 (baseline), visit 5/week 4 and visit 8/week 14 (EoS) only if an AE related to hematology, biochemistry or urinalysis parameters occurred since the previous visit or at the discretion of the investigator. If any of the clinical laboratory tests results are outside the normal range at any scheduled time point during the study, the investigator may decide to repeat the test(s) on new samples. The clinical relevance of the abnormal results will be documented. Clinically relevant changes will be recorded as AEs (see Section 7.3 of protocol: Adverse Events and Other Safety Aspects).

The laboratory parameters that will be assessed during the conduct of the study are listed in Table 5.

Hematology	Biochemistry	Urinalysis			
Hematocrit	Albumin	Leukocyte esterase			
Hemoglobin	Alanine aminotransferase	Nitrites			
Mean corpuscular volume	Alkaline phosphatase	pH			
Mean corpuscular hemoglobin	Aspartate aminotransferase	Protein			
Mean corpuscular hemoglobin	Bicarbonate	Red blood cells			
concentration	Blood urea nitrogen				
Platelets	Calcium				
Red blood cell count	Chloride				
White blood cell count	Corrected serum calcium				
White blood cell count differential	Creatinine				
	Creatinine kinase				
	Glucose				
	Lactate dehydrogenase				
	Magnesium				
	Phosphate				
	Potassium				
	Serum hCG for female subjects				
	Sodium				
	Total bilirubin (total and direct)				
	Total protein				
hCG [•] human chorionic gonadotropin					

Table 5Laboratory Assessments

The value of each hematology and biochemistry parameter will be compared to its normal range and classified as High, Low or Normal. Urinalysis parameters will be similarly classified as either Normal or Abnormal.

When calculating changes or shifts in a result from baseline, the value from visit 1 will be used as baseline. If the visit 1 value is missing, the latest pre-baseline value will be used (i.e., from Visit 1 or any unscheduled visit conducted between visit 1 and 3).

